### 7.2. Setting

Subjects will be enrolled by continuous registration method. The investigators will assess all the subjects in their practice who receive at least 1 dose of Sayana® 104mg/0.65mL agreed to participate in this study by signing the 'data privacy statement'. All subjects enrolled should meet the usual prescribing criteria for as Sayana® per the local product document and should be entered into the study at the investigator's discretion.

A written, Pfizer and institutional review board (IRB)/independent ethics committee (IEC)-approved, informed consent (ie, Data privacy statement) must be obtained before initiating study procedures.

The eligibility of the subject will be evaluated. After inclusion of the subject and after obtaining written informed consent (ie, Data privacy statement) (prior to any procedure being performed) from the subject or subject's parents/ legal representative (as appropriate), the investigator or site staff will record the subject data into source documents and into a Case Report Form (CRF). Enrollment visit is the visit when subject signs on informed consent (ie, Data privacy statement). Following the baseline data collection , the visits are at the discretion of the investigator and may follow the local usual standard of care, however, the sponsor recommends safety and treatment data

assessments at 3 month intervals (every 12~14weeks) at a minimum during the 6 months of participation. A Follow-up Call is to be conducted by investigator or delegated staffs at least 28 calendar days after the last administration of the study drug within the observational period in order to collect information on the occurrence of adverse events and concomitant medications.

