### 7.3.1.5. Administrative Status for Sayana®

Sayana® is provided by the investigator's prescription, and Pfizer Korea will not provide Sayana® for this study.

Record the following with regard to administrative status of Sayana®.

- Date of administration: Record the date of each Sayana® therapy (year/ month/day).
- Dose: Record the dose (ml).
- Outcome of administration:  
Record the evaluation date. If the purpose of administration was the prevention of pregnancy in women of child bearing potential, check either pregnant or not pregnant with the method of pregnancy check. If the subject is pregnant, record the first day of last menstrual period to collect the time to pregnancy. (At the time of first Sayana® administration, investigator must ensure the subject is non-pregnant. Also if a sexually active subject is having regular menstrual cycle and was previously not being administered with other contraceptive agent (therefore is having normal menstrual cycle), investigator must ensure that the first Sayana® injection is within 5 days of the subject's normal menstrual cycle. If the subject was previously being administered with other contraceptive agent(s) and is not having normal menstrual cycle, investigator must ensure that the subject is not pregnant by a method decided by the investigator).

If the purpose of administration was management of endometriosis-associated pain, visual analogue scale scores recorded by the subject.

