Follow-up is conducted to obtain general information on the pregnancy; in addition, follow-up is conducted to obtain information on EDP outcome for all EDP reports with pregnancy outcome unknown. A pregnancy is followed until completion or until pregnancy termination (e.g., induced abortion) and Pfizer is notified of the outcome. This information is provided as a follow up to the initial EDP report. In the case of a live birth, the structural integrity of the neonate can be assessed at the time of birth. In the event of a termination, the reason(s) for termination should be specified and, if clinically possible, the structural integrity of the terminated fetus should be assessed by gross visual inspection (unless pre-procedure test findings are conclusive for a congenital anomaly and the findings are reported).

If the outcome of the pregnancy meets the criteria for an SAE (e.g., ectopic pregnancy, spontaneous abortion, intrauterine fetal demise, neonatal death, or congenital anomaly [in a live born, a terminated fetus, an intrauterine fetal demise, or a neonatal death]), the procedures for reporting SAEs should be followed.

Additional information about pregnancy outcomes that are reported as SAEs follows:

- Spontaneous abortion includes miscarriage and missed abortion;

- Neonatal deaths that occur within 1 month of birth should be reported, without regard to causality, as SAEs. In addition, infant deaths after 1 month should be reported as SAEs when the investigator assesses the infant death as related or possibly related to exposure to investigational product

Additional information regarding the exposure during pregnancy may be requested. Further follow-up of birth outcomes will be handled on a case-by-case basis (e.g., follow-up on preterm infants to identify developmental delays).

In the case of paternal exposure, the study participant will be provided with the Pregnant Partner Release of Information Form to deliver to his partner. It must be documented that the study participant was given this letter to provide to his partner.

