8.2.2 Efficacy Analysis

The cumulative percent of patients who become pregnant by month 6 will be calculated as $100*(1 - \text{Kaplan-Meier curve at month 6})$, where the Kaplan-Meier (KM) method for estimating survival function will be applied to time-to-pregnancy. Patients who did not become pregnant will be censored at the time of their last follow-up. The KM method will also be used to calculate a 95% confidence interval for this cumulative percent at month 6.

[figure not shown]
[figure not shown]
The rate of pregnancies per 100 person-years of follow-up will be summarized by a 95% confidence interval.

For the rate of pregnancies per 100 person-years of follow-up defined as major events, incidence rate will be calculated as follows:

$100 \times (\text{total number of patients with effectiveness endpoint}) / (\text{total person-years of patients included in the effectiveness analysis set})$ where total person-years is equal to (last evaluation date of outcome - first date of administration +1)/365.25 for all patients in the effective analysis set

The difference between the visual analogue scale (VAS) endometriosis pain scores measured at each visit and the measurement taken before the administration of Sayana[®] will be analyzed using paired t-test.

PFIZER CONFIDENTIAL

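### Kaplan-Meier and the pregnancy rate end follow-up on different dates: one is undefined, the other runs past the pregnancy

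*SAP*

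**What the plan says.** For the cumulative percent at month 6, SAP section 8.2.2 states: "Patients who did not become pregnant will be censored at the time of their last follow-up". Protocol section 7.7.2.2 has the same rule. Neither document says which contact counts as last follow-up.

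For the rate per 100 person-years, the same SAP section builds the denominator from "last evaluation date of outcome - first date of administration +1", divided by 365.25 and applied to every patient in the analysis set. It makes no exception for women who become pregnant.

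Protocol section 7.3.1.5 describes the outcome record for women using the product for contraception. The investigator enters an evaluation date and must "check either pregnant or not pregnant with the method of pregnancy check". It adds: "If the subject is pregnant, record the first day of last menstrual period to collect the time to pregnancy".

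Protocol section 7.2 leaves visits to the investigator and recommends assessments at three-month intervals. It also requires a Follow-up Call "at least 28 calendar days after the last administration of the study drug within the observational period", made "in order to collect information on the occurrence of adverse events and concomitant medications". SAP section 5.2 admits a woman to the efficacy set with as little as one outcome evaluation.

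**The concern.** The cumulative percent and the rate are two of the three effectiveness parameters in protocol section 7.7.1.3, and they should describe the same women over the same time at risk. As written they need not.

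- **Kaplan-Meier.** A woman checked once at about month 3, with a later contact at which pregnancy status is not recorded, can be censored at that later contact. She then sits in the risk set as pregnancy-free for time in which nobody checked.
- **Rate.** The clock runs to the last outcome evaluation even for a woman found pregnant there. The time between the start of her pregnancy and that evaluation is not time at risk.

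Each adds to the denominator without adding events, so each can only lower the estimate or leave it unchanged. Because last follow-up is undefined, two programmers could also follow section 8.2.2 faithfully and report different Kaplan-Meier values.

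**Working it through.** The documents state no expected pregnancy rate, and the 600 subjects are a regulatory minimum, so there is no figure of the plan's own to reproduce. Pregnancy rates and counts, lags and shares of women unchecked are assumptions.

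**1. Person-time after pregnancy (rate).** Inputs: 600 women (protocol section 7.5), 0.5 year each (protocol section 7.1). Assumed: d pregnancies, last menstrual period at 0.25 year, and a lag of L weeks from then to the evaluation.

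Person-years stopped at pregnancy = (600 − d) × 0.5 + d × 0.25. The SAP formula adds d × 7L / 365.25.

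- d = 1, L = 4: 299.75 becomes 299.83; the rate falls by 0.03% relative.
- d = 3, L = 13: 299.25 + 3 × 91/365.25 = 300.00; the rate goes from 1.003 to 1.000 per 100 person-years (0.25% relative). The exact Poisson 95% interval is 0.207 to 2.930 against 0.206 to 2.922.
- d = 12, L = 13: 297.00 becomes 299.99; the rate goes from 4.040 to 4.000 (1.0% relative).
- d = 0: no change.

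**2. Censoring date (Kaplan-Meier).** Assumed: constant hazard λ = 0.02 per year; a share f of women last checked at day 91 with their last contact at day c; no pregnancy after day 91 detected among them; everyone else checked to day 183.

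Between day 91 and day c these women are in the risk set but cannot produce an event, so the observed hazard is about (1 − f)λ. After day c they leave and it returns to λ. Hence

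estimate ≈ 1 − exp{−(0.02/365.25) × [183 − f(c − 91)]}.

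| End date for the unchecked women | f = 20% | f = 43% |
|---|---|---|
| Day 91 (last pregnancy check) | 183 days: 0.997% | 183 days: 0.997% |
| Day 119 (28 days after a day-91 dose) | 183 − 5.6 = 177.4: 0.97% | 183 − 12.04 = 170.96: 0.93% |
| Day 183 (month 6) | 183 − 18.4 = 164.6: 0.90% | 183 − 39.56 = 143.44: 0.78% |

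**3. Cross-check on a finite sample.** Take 600 women and 3 observed pregnancies, at weeks 4, 14 and 24, with some of the 597 others unchecked after week 13.

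- 10% unchecked (60 women), censored at week 13: 1 − (599/600)(538/539)(537/538) = 0.54%. Censored at week 17: 1 − (599/600)(598/599)(537/538) = 0.52%. Censored at week 26: 1 − 597/600 = 0.50%.
- 50% unchecked (298 women): 0.83%, 0.67% and 0.50% respectively.

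The direction agrees with step 2. With no pregnancies, the Kaplan-Meier point estimate is zero whichever date is used.

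**The case against.** Two stronger readings are tempting, and the documents support neither.

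A reader might infer that last follow-up is the Follow-up Call and that the call leaves pregnancy out. The documents do not say that the call is the final contact or that it sets the censoring date. After a month-3 injection it could fall around month 4, before a month-6 visit. Pregnancy is not a named purpose of the call, but exposure during pregnancy must be recorded on the case report form and reported to the sponsor (protocol sections 9.1 and 9.2.3), so a call could reveal one. A pregnancy that might be mentioned is still not the same as a recorded negative status.

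A reader might also infer many months of extra person-time per pregnancy from the statement "A pregnancy is followed until completion or until pregnancy termination". That sentence governs safety reporting. The outcome evaluation is the pregnancy check of protocol section 7.3.1.5, within a six-month observation period, so a lag of weeks is the supportable range.

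It can further be argued that section 8.2.2 already equates follow-up with time to the last outcome evaluation, because its person-years of follow-up are computed that way. On that reading the two end dates agree for women who do not become pregnant. This is a reasonable interpretation, but it is not stated, and the Kaplan-Meier sentence uses a different term. It also leaves the missing stop at pregnancy untouched.

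Finally, the month-6 row of the table is an upper bound within the assumed shares, which have no source in the documents. The analyses are primarily descriptive, and no decision rule rests on either pregnancy estimate. Both points stand and limit the consequence.

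**Conclusion.** The defect holds. Section 8.2.2 uses two end dates, one undefined and one with no stop at pregnancy, and any resulting error is downward. The rate formula is wrong as written, but the error is far smaller than the width of the confidence interval.

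The censoring date is the more material part. On the assumptions shown, the understatement runs from about 0.03 percentage points (day 119, 20% unchecked) to about 0.21 (month 6, 43% unchecked) on a true risk of 1.0%. It shrinks if sites check most women near month 6, if later pregnancies come to light, or if programmers already read last follow-up as the last pregnancy check. If no pregnancies occur, neither point estimate moves. The point is worth settling before the final analysis because the correction is nearly free.

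**What to change.** In SAP section 8.2.2, state one rule for both estimates:

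- For a woman who becomes pregnant, time at risk ends at the pregnancy date, derived by a stated rule from the recorded first day of the last menstrual period. The rule should cover a recorded date that falls before the first dose.
- For all other women, time at risk ends at the last date on which pregnancy status was assessed.
- A contact without a recorded pregnancy status does not extend time at risk.
- Kaplan-Meier is read at month 6.

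This is SAP wording only and uses dates already collected. Protocol section 7.7.2.2 allows the SAP to modify the outlined analyses. The cost is slightly less time at risk and a slightly wider interval.

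Adding a pregnancy question to the Follow-up Call is optional and not part of this fix. It would need a protocol change with ethics approval. With SAP version 2.0 dated April 2020 and the study running to 28 January 2021, it could reach only the calls still to be made.

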**Figure 1. Data Management Flow Chart**

**Figure 2. Data Validation Flow Chart**

## 7.7. Data analysis

### 7.7.1. Assessment of Safety and Effectiveness Parameters

#### 7.7.1.1. Analysis Populations

All analyses will be performed on the safety population, defined as those patients who took at least one dose of study medication.

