#### 7.7.1.3. Effectiveness Parameters

Effectiveness parameters include:

- Cumulative percent of patients who become pregnant over the 6 month observation period.
- Rate of the number of pregnancies per 100 per-years of follow-up.
- Change from baseline in visual analogue scale (VAS) endometriosis pain scores at each visit.

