## 7.7.2. Statistical Considerations

Statistical analyses of safety and effectiveness parameters will be primarily descriptive in nature; no statistical hypotheses will be tested. No imputations for missing data are planned.

As required by MFDS regulations, the periodic report should be submitted to MFDS every 6 months for the first two years and then annual report should be submitted to MFDS for the third, fourth and fifth year. The final report should be submitted in the sixth year. Interim analysis will be performed in time for the report submission.

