#### **7.7.2.2. Effectiveness Analyses**

- The cumulative percent of patients who become pregnant by month 6 will be calculated as  $100*(1 - \text{Kaplan-Meier curve at month 6})$ , where the Kaplan-Meier (KM) method for estimating survival function will be applied to time-to-pregnancy. Patients who did not become pregnant will be censored at the time of their last follow-up. The KM method will also be used to calculate a 95% confidence interval for this cumulative percent at month 6.
- The rate of pregnancies per 100 person-years of follow-up will be accompanied by an 95% confidence interval; this confidence interval will be based on the Poisson distribution.
- Mean change in VAS scores from baseline will be tested against zero change using the paired t-test; p-values  $\leq 0.05$  will indicate statistically significant change. Mean change will also be described using a 95% confidence interval.

Detailed methodology for summary and statistical analyses of data collected in this study will be documented in a SAP, which will be dated, filed and maintained by the sponsor. The SAP may modify the plans outlined in the protocol; any major modifications of primary endpoint definitions or their analyses would be reflected in a protocol amendment.

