5.2 EFFICACY ANALYSIS SET

Subject who have been administered Sayana® at least once and evaluated upon its related efficacy endpoints at least once will be included in the efficacy analysis set. The efficacy analysis set is a subset of the safety analysis set.

The following cases are excluded from the efficacy analysis set:

- Subjects excluded from safety analysis set listed in section 5.1
- If the purpose of administration was the prevention of pregnancy in women of child bearing potential, subjects whose check either pregnant or not pregnant at evaluation date on the CRF are not completed
- If the purpose of administration was management of endometriosis-associated pain, subjects whose record VAS score at baseline or evaluation date on the CRF are not completed

Unless specified otherwise, statistical analysis on efficacy parameters will be performed on the efficacy analysis set.

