7 HANDLING OF MISSING VALUES

No imputation of missing data will be performed. Missing or incomplete data will be excluded from the analyses.

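### The VAS pain analysis uses only women with a score at each visit and nothing in the plan would show selective loss, so mean improvement may be overstated if women with unrelieved pain stop returning

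*SAP*

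**What the plan says.** The VAS effectiveness parameter is "Change from baseline in visual analogue scale (VAS) endometriosis pain scores at each visit" (Protocol 7.7.1.3). Protocol 7.7.2.2 states that "Mean change in VAS scores from baseline will be tested against zero change using the paired t-test", with a 95% confidence interval and significance at p of 0.05 or below. SAP 8.2.2 applies the test visit by visit: "The difference between the visual analogue scale (VAS) endometriosis pain scores measured at each visit and the measurement taken before the administration" of Sayana.

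On missing scores, the protocol says "No imputations for missing data are planned" (7.7.2), and the SAP says "Missing or incomplete data will be excluded from the analyses" (section 7). SAP 5.2 also removes from the efficacy set "subjects whose record VAS score at baseline or evaluation date on the CRF are not completed". Protocol 7.7.1.1 reads differently: "All analyses will be performed on the safety population, defined as those patients who took at least one dose of study medication". The two populations differ, but a paired test cannot use a woman without both scores whichever one governs.

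No visit calendar is fixed: after baseline, "the visits are at the discretion of the investigator" (Protocol 7.2), with assessment about every three months recommended. The design is non-comparative with six months of observation (Protocol 7.1). The minimum of 600 subjects (Protocol 7.5) covers both indications together; the number treated for endometriosis pain is not given.

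**The concern.** A paired test at each visit on the pairs that happen to exist is an available-case analysis. A woman with a poor first follow-up score who does not return counts at the first visit and is absent from the second. The second-visit mean then describes those who came back. It estimates the mean for all treated women only if coming back is unrelated to how much pain improved.

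That assumption is neither stated nor examined. Sayana is obtained on ordinary prescription (Protocol 7.3.1.5) and each further score needs a further visit, so having a score is tied to staying in care. There is no control arm in which similar loss might offset the effect. The plan has no repeated-measures model, no missing-data sensitivity analysis and no comparison of women with and without later scores. At stake is the credibility of the only planned estimate of effect in one of the two indications.

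**Working it through.** The plan states no effect size, SD, dropout rate or number of women for VAS, so there is no figure to reproduce. All numerical inputs below are assumptions.

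**1. Identity.** Let d be the share of women without a score at a visit, S the mean improvement in women with a score, and L the mean improvement in those without. The mean over all women is (1 - d)S + dL, so

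observed mean - all-women mean = d × (S - L).

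| Share missing | L is 10 to 30 mm smaller than S | L equals S | L is 10 to 20 mm larger than S |
|---|---|---|---|
| 10% | overstated by 1 to 3 mm | 0 | understated by 1 to 2 mm |
| 20% | overstated by 2 to 6 mm | 0 | understated by 2 to 4 mm |
| 30% | overstated by 3 to 9 mm | 0 | understated by 3 to 6 mm |
| 40% | overstated by 4 to 12 mm | 0 | understated by 4 to 8 mm |

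**2. Loss that depends on a recorded early score.** Assume 150 women, 70% responding by -35 mm at visit 2 and 30% unchanged. The true mean change is 0.7 × (-35) = -24.5 mm. Each woman's changes have a shared SD of 12 mm plus a residual SD of 12 mm per visit. Women improving by less than 10 mm at visit 1 miss visit 2 with probability 0.3 to 0.7, the others with probability 0.1. Responders' visit-1 effect was varied from 60% to 100% of the visit-2 effect.

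- Planned visit-2 mean: about -26 mm (at 0.3) to -30 mm (at 0.7).
- Likelihood estimate, using the visit-1 change to predict the visit-2 change: about -24.5 to -25.2 mm.

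**3. False significance with no true change.** Keep the same SDs and split loss by the sign of the visit-1 change. The SD of a change is √(144 + 144) = 16.97 mm, and the correlation between visits is 144/288 = 0.5. The mean visit-2 change given a visit-1 change on one side of zero is ±0.5 × 16.97 × 0.798 = ±6.77 mm.

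- 50% versus 10% loss: 0.25 + 0.45 = 0.70 of women remain. Bias = 6.77 × (0.25 - 0.45)/0.70 = -1.93 mm.
- 30% versus 10% loss: 0.35 + 0.45 = 0.80 remain. Bias = 6.77 × (0.35 - 0.45)/0.80 = -0.85 mm.

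For 150 women and 50% versus 10% loss, the standard error is 16.97/√105 = 1.66 mm. The shift is 1.93/1.66 = 1.17 standard errors, which gives about a 21-22% chance of p ≤ 0.05. Simulated values, which vary by about one percentage point between runs:

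| Loss | 60 women | 150 women |
|---|---|---|
| 30% versus 10% | about 6% | about 8% |
| 50% versus 10% | about 12% | about 21% |

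The nominal level is 5%.

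**4. Loss that depends on the unrecorded score itself.** Assume a true mean reduction of 20 mm, SD 25 mm, and log-odds of leaving that rise by 1 for each SD of less relief. The observed mean reduction is 22.2, 24.4, 26.3 and 28.3 mm at 10, 20, 30 and 40% missing. With the dependence reversed it is 17.8, 15.7, 13.6 and 11.7 mm. With no true change and 20% missing, the chance of p ≤ 0.05 is about 22%, 39% and 66% for 50, 100 and 200 women. The answer therefore turns on the assumed mechanism and numbers.

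**The case against.** A reader might infer that the plan does overstate pain relief. The documents do not support that. They give no dropout rate and no reasons for leaving, and nowhere say that return visits follow satisfaction with treatment. Women may also miss a visit because of adverse events, cost or resolved pain, and the same arithmetic then gives no bias or understatement. This part of the objection stands, and the point is conditional for that reason.

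A reader might also infer that attrition could produce a false positive finding with consequences. Protocol 7.7.2 calls the analyses mainly descriptive, and SAP section 4 declares hypotheses and decision rules not applicable. A p-value is still planned and a 5% level set (Protocol 7.7.2.2, SAP 9.1), but no decision rests on it. At the milder loss rates the inflation is small. In the benefit scenario, a change of -26 to -30 mm in place of -24.5 mm is a large reduction either way.

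Some attrition would be visible. SAP 8.1.1 includes n in continuous summaries, the Basic Results tables count starters and completers, the reason for withdrawal is to be asked (Protocol 8.2), and lack of efficacy is recorded (Protocol 9.1). None of these enters the VAS analysis or shows whether the women without later scores had less relief.

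Finally, a mixed model is no complete cure. It works well in step 2 because loss there depends only on a recorded score. It does not correct for loss driven by pain after the last score, nor for women with no post-baseline score. This also stands, and the fix allows for it.

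**Conclusion.** The point holds conditionally. The VAS analysis is available-case at each visit and rests on an unstated assumption that nothing planned would test. Later-visit improvement is overstated if women with unrelieved pain stop returning, understated if women leave after relief, and unbiased if loss is unrelated to pain.

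Under the assumed 30-70% versus 10% loss by early response, the overstatement is about 1.5 to 5.5 mm on a true 24.5 mm, and a likelihood analysis removes most of it. With no true change, false significance lies between about 6% and 21% over the loss rates and numbers of women in step 3; the mechanism in step 4 gives higher values. None of the rates, SDs or numbers of women comes from the documents, so neither the direction nor the size in this study can be established from them. The change is worth making because it is cheap and uses scores already collected, not because bias has been shown.

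**What to change.** In SAP 8.2.2, make the VAS analysis a mixed model for repeated measures on all post-baseline scores. Use prespecified windows of time since first dose, a rule for choosing one score per window, baseline VAS as covariate and within-woman correlation. Report mean change with a 95% confidence interval for each window. Keep the per-visit paired summaries as descriptive output.

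Because the model does not correct for women removed under SAP 5.2 for having no post-baseline score, or for loss driven by unrecorded pain, also report:

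- the number of women scored in each window, against all women treated for endometriosis pain;
- reasons for missing scores, where recorded;
- baseline and last available VAS for women with and without a later score.

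With these counts, a reader can apply d × (S - L) for any assumed gap between the two groups.

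The model needs no imputation, so it fits Protocol 7.7.2, and Protocol 7.7.2.2 lets the SAP modify the planned analyses. The cost is SAP wording, one SAS procedure and a few tables on existing data. Windows must be chosen because visits are unscheduled, and they should take account of the three-month recall in the VAS question (Protocol 7.1.2). The reported improvement may turn out smaller.

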#### 7.1.2. Effectiveness Endpoints

- Cumulative percent of patients who become pregnant over the 6 month observation period and rate of pregnancies per 100 person-years of follow-up.
- The patient response to endometriosis pain treatment: endometriosis pain treatment effect will be measured by visual analogue scale scores recorded by the subjects at each visit. The subject will be asked to indicate the subjective level of endometriosis pain looking back at the last 3 months and mark it with a single vertical mark on the 100mm horizontal visual analogue scale, where 0 mm represents absence of pain and 100mm indicates unbearable pain.

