### 7.3.1. Data Collection

The investigator will observe each enrolled subject for 6 months, prospectively, from the enrollment date. There is no specified visit schedule, because this study is not an interventional study. Safety information will be collected at every visit performed for the subject during the observation period.

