9 APPENDICES

9.1 APPENDIX 1: NOTES

- All statistical summaries and analyses will be carried out using SAS Software version 9.2 or higher.
- Where formal statistical tests are performed, significance will be declared using a 2-sided 5% level of significance

PFIZER CONFIDENTIAL

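### VAS change is tested at each visit with a 3-month recall question and no analysis windows, so any score before about 13 weeks includes pre-dose pain and visit number has no common time meaning

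*SAP*

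**What the plan says.** Protocol 7.1.2 measures the endometriosis effect by "visual analogue scale scores recorded by the subjects at each visit". At each one the woman is asked to "indicate the subjective level of endometriosis pain looking back at the last 3 months".

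Protocol 7.7.1.3 makes the parameter "Change from baseline in visual analogue scale (VAS) endometriosis pain scores at each visit". For the analysis, Protocol 7.7.2.2 says "Mean change in VAS scores from baseline will be tested against zero change using the paired t-test" and adds a 95% confidence interval. SAP 8.2.2 applies the paired t-test to the difference between the VAS "endometriosis pain scores measured at each visit and the measurement taken before the administration" of Sayana, and SAP 9.1 adds that "significance will be declared using a 2-sided 5% level of significance".

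On timing, Protocol 7.3.1 says "There is no specified visit schedule, because this study is not an interventional study", and Protocol 7.1 leaves the interval to the investigator. Protocol 7.2 and SAP 2.1 record a sponsor recommendation that safety and treatment data be assessed at least every 12 to 14 weeks during the 6 months. The SAP gives no analysis window for VAS, no minimum time since first dose, and no rule for which visit counts.

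**The concern.** The recall period is as long as the recommended visit interval. A woman seen earlier than that is asked about a period that began before her first injection and that overlaps the period her baseline score described. The difference between the two scores then compares partly the same time, and the mean change moves towards zero.

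A second problem does not depend on how women recall pain. With no schedule and no windows, the first post-baseline visit may fall at week 4 for one woman and week 14 for another. A mean change at that visit has no fixed time meaning. Missing data are not imputed (SAP 7), so means at later visits come only from women who attended that often.

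VAS change is the only effectiveness measure for the endometriosis indication. In the same SAP section the cumulative pregnancy percentage is fixed at month 6, while VAS has no time anchor. Without one, the choice of which visit represents the VAS result is left until after the data are seen.

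**Working it through.** The documents give no VAS effect size, standard deviation, power or number of endometriosis patients, so there is no planned figure to reproduce. The check is the overlap between the recall window and the time before the first dose.

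**Inputs**
- Recall period W: 3 months (Protocol 7.1.2), taken as 365.25/4 = 91.3 days, with 84 to 98 days as a sensitivity range.
- Time t: days from first dose to the VAS score. It is not fixed by the documents.
- Recommended assessment interval: 12 to 14 weeks, so t = 84 to 98 days (Protocol 7.2, SAP 2.1).

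**Formula**
- Post-dose share = min(1, t/W). Pre-dose share = 1 − post-dose share.

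| Score taken at | t (days) | Pre-dose share, W = 91.3 |
|---|---|---|
| week 2 | 14 | 85% |
| week 4 | 28 | 69% |
| week 6 | 42 | 54% |
| week 8 | 56 | 39% |
| week 10 | 70 | 23% |
| week 12 | 84 | 8% |
| week 13 | 91 | 0.3% |
| week 14 and later | 98 or more | 0% |

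For example, at week 4: 1 − 28/91.3 = 69%.

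**Where most of the window is pre-dose.** This holds for t < W/2 = 45.7 days, about 6.5 weeks. With W from 84 to 98 days the limit is 6.0 to 7.0 weeks.

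**Where the recommendation is followed.** At weeks 12 to 14 the pre-dose share is 0 to 8%. With W = 98 days the week-12 value is 1 − 84/98 = 14%, so the range over all W tried is 0 to 14%. At about month 6 it is zero.

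**Illustration in millimetres.** Assume a true fall of 20 mm, equal weight on every day recalled, and full effect from day 1. Observed fall = 20 × post-dose share:
- week 4: 20 × 0.307 = 6 mm
- week 8: 20 × 0.613 = 12 mm
- week 12: 20 × 0.920 = 18 mm
- week 14 onwards: 20 mm

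**Mixed timing within one visit.** If half the women had their first post-baseline visit at week 4 and half at week 13, the share of the true change seen would be 0.5 × 0.307 + 0.5 × 0.997 = 65%. This split is hypothetical.

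**The case against.** The strongest reply is that the recommended 12 to 14 week interval matches both the recall period and the injection interval in SAP 5.1. Sites that follow it produce scores with little or no overlap, and only about two post-baseline assessments in 6 months. Other text also suggests fewer early scores than a reading of each visit implies. Protocol 7.3.1.5 places VAS under the outcome of administration, with an evaluation date, and SAP 5.2 refers to baseline or evaluation date. The follow-up call at 28 days or later collects adverse events and concomitant medications, not VAS. The analyses are mainly descriptive, VAS concerns one indication only, and this dilution would understate benefit rather than create a false positive.

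Most of this stands and limits the size of the problem. It does not remove it. The interval is a recommendation, Protocol 7.1.2 still has VAS recorded at every visit, and no SAP rule excludes an early score from the test.

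A reader might infer three stronger claims, and the documents do not support them:
- *Post-baseline scores mostly reflect pre-dose pain, or the VAS result as a whole is materially diluted.* The first is true only before about 6.5 weeks. The second depends on how often early scores occur, which is not stated.
- *The SAP departs from the protocol.* It follows the parameter in Protocol 7.7.1.3.
- *The SAP pools scores by visit number.* It does not say so in those words. However, it tests at each visit and offers no other time basis.

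**Conclusion.** The point holds in limited form. Any VAS score before about 13 weeks after the first dose includes pre-dose time, and before about 6.5 weeks that is more than half of the recall window. Where the 12 to 14 week recommendation is followed, the pre-dose share is about 0 to 8% (0 to 14% across the recall lengths tried), and it is nil at month 6. The recommendation is not binding, and the stated rule, applied literally, tests early scores as they come and gives visit means without a common time meaning.

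The window shares rest only on the length of the recall period. Turning them into dilution also assumes even recall and full effect from day 1. Women who weight recent pain more heavily would show less dilution. The millimetre figures are illustrations, and the overall dilution cannot be computed from the documents.

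**What to change.** In SAP 8.2.2, with matching wording in Protocol 7.7.1.3, define the VAS analysis by time since first dose, using contiguous windows. For example:
- Month 3: the score closest to day 91 within days 84 to 136.
- Month 6: the score closest to day 182 from day 137 to the end of the observation period.

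Day 84 is week 12, the lower end of the recommended interval. The boundary is the midpoint of the two targets, (91 + 182)/2 = 136.5. Because the windows are contiguous, no score from day 84 onwards is left unassigned.

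Base the paired t-test and the 95% confidence interval on these two windows. List or summarise scores before day 84 descriptively, without testing them.

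The cost is wording in both documents. Administration and evaluation dates are already collected (Protocol 7.3.1.5), so no new data and no change to visits are needed. The downside is that women whose only post-baseline score falls before day 84 contribute no tested VAS result. Their number should be reported.
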